9.7.2 Measures of occurrence and measures of association

Prevalence of each outcome will be computed as number of observations with a given outcome divided by the total number of study population members. For neonatal death, a 28-day mortality risk will be the measure of occurrence among live-born infants. Prevalence/risks will be compared according to predefined exposure categories and using, whenever necessary,

plausible exposure risk windows. For example, for assessing the outcome of congenital malformations, births will be classified based on their exposure in the first trimester. For all other neonatal outcomes, exposure any time in pregnancy and per trimester may be considered.

Table 4 summarizes outcome-specific analysis populations and exposure windows.

Table 4 Summary of outcome-specific analysis populations and relevant exposure windows

Outcome	Analysis population	Relevant exposure window
Hypertensive disorders of pregnancy (preeclampsia, eclampsia, gestational hypertension)	All pregnancies	1st or 2nd trimester
Gestational diabetes	All pregnancies	1st or 2nd trimester
Bleeding during pregnancy	All pregnancies	1st or 2nd trimester
Postpartum haemorrhage	All pregnancies	Any time during pregnancy
Pregnancy-related death	All pregnancies	Any time during pregnancy
Fetal death (spontaneous abortion or stillbirth)	A combined population of stillbirths, livebirths, and pregnancies ending in a spontaneous abortion	Any time during pregnancy
Termination of pregnancy for fetal anomaly (TOPFA)	All pregnancies	Any time during pregnancy
Any elective pregnancy termination	All pregnancies	Any time during pregnancy
Ectopic pregnancy	All pregnancies	Any time during pregnancy
Fetal growth restriction/small for gestational age (SGA)	Live births	Any time during gestation
Preterm birth (<37 full gestational weeks)	Live births	Any time during gestation
Low birth weight (<2500 g)	Live births	Any time during gestation
Major congenital malformations	Live or stillbirths/TOPFA (whenever available) without evidence of teratogenic exposure or infection or chromosomal anomaly	First trimester
Microcephaly (based on head circumference)	Live births without evidence of teratogenic exposure or infection or chromosomal anomaly	Any time during gestation
Low 5-minute Apgar score	Live births	Any time during gestation
Neonatal death (death within 28 days of birth)	Live births	Any time during gestation

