The maternal and pregnancy outcomes will be addressed using the prevalence study design; neonatal outcomes and pregnancy related death in the cohort design. In the routinely collected data, pregnancies are typically identifiable on the date of pregnancy end, either in a birth or in an abortive outcome. All identifiable pregnancies will be included, and their start and end dates will be determined based on the LMP or gestational age at end, depending on data availability. Outcomes examined in this design include gestational diabetes, hypertensive disorders of pregnancy, pregnancy-related death, fetal growth restriction/small for gestational age, spontaneous abortion, stillbirth, preterm birth, major congenital malformations, microcephaly, neonatal death, and termination of pregnancy for foetal anomaly (TOPFA).

Population

This study will be multi-database, utilizing routinely collected health data of various types in five European countries: Denmark, Italy, Norway, Spain, and the United Kingdom. Pregnancies ending between 6 January 2021 (date of the earliest approval of the COVID-19 Moderna Vaccine in Europe) and 31 December 2022 will be identified and classified according to the exposure to the COVID-19 Moderna Vaccine, overall and according to the trimester of exposure. The study period may be extended if the size of the study population is insufficient to study specific outcomes of interest.

The study population will encompass all pregnancies, identifiable in the databases, ending in a live or still birth, a spontaneous abortion, or an induced abortion, as identifiable in the participating databases. In Denmark and Norway, all pregnancies ending in a live or still birth, as well as pregnancies leading to a hospital encounter due to termination will be identifiable.

Variables

Members of the analysis populations (pregnancies, births, depending on the outcome) will be described with respect to available demographic characteristics, medical history, medication use, receipt of other vaccines, and characteristics of the exposed pregnancy. Pregnancies and births will be classified according to the exposure status Spikevax, overall and by trimester.

The outcomes of interest will include pregnancy complications, adverse pregnancy outcomes, and adverse neonatal outcomes.

Covariates will include maternal pre-pregnancy demographic and clinical characteristics, such as age, smoking, body mass index, chronic morbidities and medication use.

Data sources

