This study is planned as analysis of routinely collected health data in secondary automated electronic data sources in Denmark, Italy, Norway, Spain, and the UK, selected based on availability of the required routinely collected data, including information on vaccine brand and frequency of data updates.

Study size

It is estimated that the number of live births available for analysis will range between 20,000 to 100,000 depending on a data source.

Data analysis

Counts and percentages will be presented for categorical variables (woman's age at conception in categories). Means, standard deviations, medians and interquartile ranges will be presented for continuous variables (woman's age at conception). The proportion of missing data will be described when appropriate. For pregnancy complications and adverse pregnancy outcomes, pregnancy will be the unit of observation; for neonatal outcomes, a newborn will be the unit of observation. For the outcomes of congenital malformations and stillbirth, the number at risk will be the total number of live or stillborn children.

Prevalence of each outcome will be computed as number of observations with a given outcome divided by the total number of observations at risk. Prevalence of each outcome will be compared for exposed vs. unexposed pregnancies according to predefined exposure categories and using, whenever necessary, plausible exposure risk windows. For example, for assessing the outcome of congenital malformations, maternal gestational diabetes and hypertensive disorders, births or pregnancies will be classified based on their exposure in the first (or second, if relevant) trimester. For all other neonatal outcomes, exposure any time in pregnancy and per trimester may be considered.

For neonatal deaths, 28-day mortality risks will be computed and compared among live-born neonates. For pregnancy-related death, maternal mortality will be evaluated at any time while pregnant or up to 1 year after pregnancy end.

All relevant analyses will be stratified by country, maternal age, sex, calendar time, trimester and seasonality if applicable.

Milestones

Data collection will continue through 31 March 2023 with a final study report planned by December 2023.

5. Amendments and updates

Write "None" or indicate any substantial amendment and update to the study protocol after the start of data collection in a table as indicated below.

Confidential

Post-marketing safety study for COVID-19 mRNA-1273 vaccine

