9.1. Study design

9.1.1 Prevalence study

The pregnancy complications, adverse pregnancy outcomes (except pregnancy-related death), and neonatal outcomes (except neonatal death) will be addressed using the prevalence study

design. In the routinely collected data, pregnancies are identifiable on the date of pregnancy end, either in a birth or in an abortive outcome. All identifiable pregnancies will be included, and their start and end dates will be estimated based on the first day of the last menstrual period (LMP) or gestational age at end, depending on data availability. Outcomes examined in this design include gestational diabetes, hypertensive disorders of pregnancy, fetal growth restriction/small for gestational age, abortive outcomes, stillbirth, preterm birth, major congenital malformations, microcephaly (head circumference), and ectopic pregnancy..

Risk of adverse and pregnancy outcomes will be compared in births exposed and unexposed to Spikevax. The measure of association will be prevalence ratio.

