9.3.2 Outcome

9.3.2.1 Primary outcomes

The following outcomes will be assessed, noting that outcome-specific analytic considerations such as the etiologically relevant exposure window and specific additional population restrictions (e.g., exclusion of women with teratogenic medication exposure or teratogenic infections for assessment of major congenital malformations) will be defined in the SAP.

- Pregnancy complications are:
 - Hypertensive disorders of pregnancy (preeclampsia, eclampsia, gestational hypertension)
 - Gestational diabetes
 - Bleeding during pregnancy
 - Postpartum haemorrhage
 - Pregnancy-related death

- Adverse pregnancy outcomes are:
 - Fetal death (spontaneous abortion or stillbirth)
 - Termination of pregnancy for fetal anomaly (TOPFA)
 - Any elective pregnancy termination
 - Ectopic pregnancy

- Adverse neonatal outcomes are:
 - Fetal growth restriction/small for gestational age (SGA), using sex- and gestational-age specific cutoffs¹³
 - Preterm birth (<37 full gestational weeks)
 - Low birth weight (<2500 g)
 - Major congenital malformations¹⁴
 - Microcephaly (based on head circumference)
 - Low 5-minute Apgar score
 - Neonatal death (death within 28 days of birth)

Where a signal is detected for the outcome of major congenital malformation as a composite, organ system-specific analyses will be conducted. Organ-specific major congenital malformations, according to the EUROCAT¹⁴ classification are:

- Nervous system
- Eye
- Ear, face and neck
- Congenital heart defects
- Respiratory

- Oro-facial clefts
- Digestive system
- Abdominal wall defects
- Urinary
- Genital
- Limb
- Other

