9.5. Study size

Table 2 shows estimated number of live births expected annually from each participating database.

Table 2 Estimated annual number of live births in each participating country/database

	Denmark	Italy	Norway	Spain	UK
Live/still births, per year	60,000	25,000	60,000	45,000	10,000

In observational studies based on routinely collected data, where investigators do not control the study size, it is of interest to estimate the magnitude of an effect that can be ruled out with the available data and its precision.¹⁵ Specifically, of interest is the magnitude of the upper 95% confidence limit that can be ruled out for an outcome, given the estimated size of the exposed/comparator groups and expected prevalence of the outcome. As proposed by Rothman and Greenland, study precision is expressed “by designing a study that gives an upper limit for the confidence interval that has a specified probability of being below a chosen value. The multiplier Z [in the calculations] is derived from the desired confidence level: Z is the value of the standard normal distribution such that the area under the curve from $-Z$ to $+Z$ equals the confidence level. Z is 1.96 for 95% confidence.” (Rothman and Greenland, p. 600).¹⁵

Table 3 Upper limit of 95% confidence interval (CI) that can be ruled out with 80% and 90% probability under different assumptions regarding proportion of vaccinated births and prevalence of outcome

Example country	Total births	Spikevax exposed births	Example outcome	Allocation ratio	Outcome prevalence in exposed	Outcome prevalence in comparator	Upper 95% CI limit, that can be ruled out with 80% probability	Upper 95% CI limit, that can be ruled out with 90% probability
Denmark or Norway (largest number of births)	100,000	16667	Cardiac malformations	5	0.01	0.01	1.27	1.31
		16667	Any major malformation	5	0.05	0.05	1.11	1.13
		16667	Small for gestational age	5	0.1	0.1	1.07	1.09

	16667	Spontaneous abortion	5	0.2	0.2	1.05	1.06	
	9091	Cardiac malformations	10	0.01	0.01	1.36	1.43	
	9091	Any major malformation	10	0.05	0.05	1.14	1.17	
	9091	Small for gestational age	10	0.1	0.1	1.10	1.11	
	9091	Spontaneous abortion	10	0.2	0.2	1.06	1.07	
	4762	Cardiac malformations	20	0.01	0.01	1.51	1.61	
	4762	Any major malformation	20	0.05	0.05	1.20	1.23	
	4762	Small for gestational age	20	0.1	0.1	1.13	1.16	
	4762	Spontaneous abortion	20	0.2	0.2	1.09	1.10	
UK (smallest number of births)	20,000	3333	Cardiac malformations	5	0.01	0.01	1.70	1.84

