9.7.1 Descriptive analyses

Counts and percentages will be presented for categorical variables (age at conception in categories, sex). Means, standard errors, medians and ranges will be presented for continuous variables (age at conception). The proportion of missing data will be described when appropriate. For maternal outcomes, pregnancy will be the unit of observation; for neonatal outcomes, a newborn will be the unit of observation. For the outcomes of congenital malformations and stillbirth the number at risk will be the total number of live or stillborn children.

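### Stillbirth is a separate outcome in 9.1.1, 9.7.1 and the abstract, but the primary outcome list and Table 4 carry it only inside a fetal-death composite that spontaneous abortion would dominate

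*Protocol*

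**What the plan says.** Stillbirth as its own outcome:

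- Section 9.1.1 lists it apart from abortive outcomes: "abortive outcomes, stillbirth, preterm birth, major congenital malformations".
- The abstract's study design paragraph does the same: "spontaneous abortion, stillbirth, preterm birth, major congenital malformations".
- Section 9.7.1 gives it a denominator: "For the outcomes of congenital malformations and stillbirth the number at risk will be the total number of live or stillborn children". The data analysis part of the abstract repeats this.

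Stillbirth inside a composite:

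- The primary outcome list in 9.3.2.1 has no stillbirth entry. Under adverse pregnancy outcomes it has "Fetal death (spontaneous abortion or stillbirth".
- Table 4 in 9.7.2 also has no stillbirth row. The population in its fetal-death row is "A combined population of stillbirths, livebirths, and pregnancies ending in a spontaneous abortion".

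Table 3 (section 9.5) uses 20% as the example prevalence of spontaneous abortion. The protocol gives no prevalence for stillbirth.

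**The concern.** Section 9.3.2.1 and Table 4 are where an analyst would look for what to estimate and in whom. Followed literally, they give no exposed-versus-unexposed comparison for stillbirth, although three other places in the protocol expect one. Stillbirth is a grave outcome that falls under primary objective (b). In the composite it is pooled with a far more frequent event, so a ratio near 1 could be read as reassurance on stillbirth while saying little about it.

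**Working it through.** **Inputs.** From the protocol: spontaneous abortion s = 0.20; exposed counts n and comparator-to-exposed ratios k (Table 3); "Z is 1.96 for 95% confidence"; true ratio 1 for the Table 3 limits. Assumed, because the protocol does not give it: stillbirth b = 0.3%, 0.4% or 0.5% of births, and no effect on spontaneous abortion.

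**Step 1: reproduce Table 3.** Upper limit = exp[(1.96 + z) × √((1−p)/p × (1/n + 1/(kn)))], with z = 0.842 for 80% and 1.282 for 90% probability. For p = 0.20, n = 16,667, k = 5, the root is √(4 × 0.0000720) = 0.01697.

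- 80%: exp(2.802 × 0.01697) = 1.049
- 90%: exp(3.242 × 0.01697) = 1.057

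Table 3 prints 1.05 and 1.06. All 48 limits in Table 3 reproduce to two decimals.

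**Step 2: make-up of the composite.** Composite prevalence = s + (1−s)b.

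| b | Composite | Share from spontaneous abortion |
|---|---|---|
| 0.3% | 0.20 + 0.80 × 0.003 = 0.2024 | 98.8% |
| 0.4% | 0.20 + 0.80 × 0.004 = 0.2032 | 98.4% |
| 0.5% | 0.20 + 0.80 × 0.005 = 0.2040 | 98.0% |

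**Step 3: effect of an f-fold rise in stillbirth.** Composite ratio = [s + (1−s)bf] / [s + (1−s)b].

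- Doubling at b = 0.4%: 0.2064/0.2032 = 1.016 (1.012–1.020 over the range of b)
- Tripling at b = 0.4%: 0.2096/0.2032 = 1.031 (1.024–1.039)
- Fourfold: 1.036–1.059
- Fivefold: 1.047–1.078

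**Step 4: power.** Crude comparison of two proportions, two-sided 5%. Table 3 counts are treated as pregnancies, so the stillbirth-alone column uses 80% of them as births (for example 16,667 × 0.80 = 13,334). Ranges run over b = 0.3–0.5%.

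| Exposed (ratio) | Composite, stillbirth tripled | Stillbirth alone, doubled |
|---|---|---|
| 16,667 (5) | 0.29–0.64 | about 1.00 |
| 9,091 (10) | 0.19–0.44 | 0.96–1.00 |
| 4,762 (20) | 0.13–0.27 | 0.82–0.95 |
| 3,333 (5) | 0.09–0.18 | 0.64–0.82 |
| 952 (20) | 0.06–0.09 | 0.35–0.47 |

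The composite faces a tripling and stillbirth alone only a doubling, yet power is higher for stillbirth alone in every row.

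**Step 5: where the dilution matters less.**

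- Larger effects: with 16,667 exposed, the composite has power 0.56–0.94 for a fourfold and 0.80–1.00 for a fivefold rise.
- Pooling: Table 2 sums to 200,000 births a year, so about 400,000 over two years. At ratio 5 that is 400,000/6 = 66,667 exposed, and a tripling has power 0.80–1.00. At ratio 20 it is 400,000/21 = 19,048 exposed, with power 0.36–0.76. The composite ratio stays at 1.02–1.04 either way.
- Fewer captured losses: if only 5% of the population were captured spontaneous abortions (an assumption), a tripling would have power 0.84–1.00 with 16,667 exposed.

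**The case against.** Table 4 presents itself as a summary, and 9.1.1 and 9.7.1 are body text. A denominator reserved for stillbirth has a use only if stillbirth is computed alone. Section 9.3.2.1 defers outcome-specific considerations to the SAP, section 9.7 defers the planned tables to it, and Annex 1 lists a planned-tables document that is not shown. So the protocol does not settle on a composite-only analysis. This stands: the fault is conflicting text, not a firm decision to drop stillbirth. But the outcome list and Table 4 are fixed in the protocol, and a SAP written from them could omit the comparison.

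A reader might also infer that the two populations cannot coexist. They can, because they belong to differently named outcomes. What is missing is an entry for stillbirth.

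The size rests on soft inputs. The 20% is an example value for precision, not an expected captured frequency. Section 9.9 says early losses without a health care record are not detectable, and Table 5 describes Norwegian birth-registry capture as pregnancies of at least 12 weeks. The stillbirth prevalence is an assumption. Both points stand, so the figures are conditional.

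Finally, the 1.05 in Table 3 is an upper confidence limit expected with 80% probability when there is no effect. It is not a detection threshold, so the conclusion relies on the power figures instead.

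**Conclusion.** The inconsistency is certain and must be reconciled. Its consequence depends on Table 4 governing, on about 20% captured spontaneous abortion, and on stillbirth at 0.3–0.5% of births. Under those conditions a two- to threefold rise in stillbirth shifts the composite by about 1–4% and would probably be missed in any single database. The closest exception is a tripling with 16,667 exposed and stillbirth at 0.5%, where power reaches 0.64.

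A reader might go further and infer that even a several-fold rise in stillbirth could not show. The figures do not support that: a four- to fivefold rise is detectable with fair to high power in the largest scenario, and a tripling is detectable if the databases are pooled at a favourable exposure ratio or if far fewer spontaneous abortions are captured. Section 9.7.6 makes pooling conditional, however, and even then the estimate would be a ratio of 1.02–1.04 that does not point to stillbirth.

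**What to change.** In 9.3.2.1 and Table 4:

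1. Add stillbirth as its own primary outcome, with live and stillborn children as the analysis population, as 9.7.1 and the abstract already have it.
2. List spontaneous abortion separately, in the population of births plus spontaneous abortions.
3. State the exposure window for each new row, as Table 4 does for the others.

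The fetal-death composite may be kept as an additional outcome; demoting it is optional. The cost is a few lines of wording and one or two more results rows per database, with no new data. The interval for stillbirth will be wider than the composite's. By the Table 3 formula with 13,334 exposed births at ratio 5, the upper limit expected with 80% probability is about 1.52 at b = 0.4%, against about 1.05 for the composite with 16,667 exposed. But it will be an interval about stillbirth.

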9.2.1 Inclusion Criteria

The study population will include all pregnancies, identifiable in the databases, ending in a live or still birth, a spontaneous abortion, an induced abortion, or an ectopic pregnancy, as identifiable in the participating databases during the study period. In Denmark and Norway, all

pregnancies ending in a live or still birth, as well as pregnancies leading to a hospital encounter due to termination will be identifiable. All pregnancies will be eligible for inclusion.

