9.3. Variables

9.3.1 Exposure

The exposure will be defined by a record of receipt of at least one dose of Spikevax during pregnancy.

For the purposes of timing of exposure, trimesters of pregnancy will be defined as follows:

- First trimester: from the first day of the last menstrual period (LMP) to LMP+97 days (both dates inclusive);
- Second trimester: from LMP+98 days to earliest of (LMP+202 days, pregnancy end) (both dates inclusive);
- Third trimester: from LMP+203 days (inclusive) until pregnancy end date (not included)

Pregnancies unexposed to Spikevax vaccine will be categorized as unexposed or as exposed to other COVID-19 vaccines and other non-COVID-19 vaccines (influenza, meningococcal disease, pneumococcal disease, rubella, shingles, tuberculosis), overall and trimester-wise. Pregnancies among women who received Spikevax before LMP will be enumerated and may be used as an additional comparator, group size permitting.

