9.7.3 Methods to control/assess confounding

Crude and adjusted measures of association will be computed comparing the exposed vs the unexposed (prevalence ratios, risk ratios, mortality rate ratios). Adjustment will be performed by the covariates measured, with LMP as the anchor date. Covariates will be included in the

appropriate regression model: log-binomial regression for prevalences and risks and Cox proportional-hazards regression for incidence rate ratios. Candidate covariates for inclusion in the analyses will vary by database. A propensity-score based adjustment may be considered and will be described in a separate Statistical Analysis Plan. Table 5 shows country-specific availability of the covariates.

Table 5 Proposed candidate covariates and data availability in participating databases

Variable/data type	AVAILABILITY OF DATA IN THE DATABASE (either via diagnosis code or procedure or treatment proxy)				
	DENMARK (NATIONAL REGISTRIES)	ITALY/ARS TOSCANA	NORWAY (NATIONAL REGISTRIES)	SPAIN/SIDIAP	UK/CPRD
Pregnancy feasibility counts for interim reports	Hospital-based ICD-10 codes for pregnancy related diagnoses or codes for prenatal visits from the Insurance registry for primary care prenatal visits	Hospital-based ICD-10 codes for pregnancy related diagnoses or codes for prenatal visits from the Insurance registry for primary care prenatal visits	All pregnancies in Norway that last at least 12 weeks are captured in the Medical Birth Registry of Norway (mandatory notification to the registry, 100% coverage)	Most pregnancies will be identifiable in primary care; some might be missed without linkage to hospital data	Pregnancy information will be available in the main primary care dataset following primary care and/or secondary care contact with the patient. This will be based on Read and/or SNOMED codes.
Country of residence	YES	YES	YES	YES	YES
Calendar year of delivery	YES	YES	YES	YES	YES
Pregnant woman's age	YES	YES	YES	YES	YES
Marital or cohabiting status	YES	To be verified	YES	To be verified	YES
Smoking	YES	To be verified	YES	YES	YES
Alcohol use (also ICD codes)	YES, IF BASED ON ICD CODES	YES	YES, IF BASED ON ICD CODES	To be verified	YES

Confidential

Post-marketing safety study for COVID-19 mRNA-1273 vaccine

Protocol mRNA-1273-P905, Date: 27 September 2021, Version 1.2

Marital status or other available socioeconomic measures	YES	YES	YES	YES Other available socioeconomic measures	YES
Gravidity	YES	YES	YES	YES	YES
Parity	YES	YES	YES	YES	YES

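### The Table 4 population for fetal death deletes pregnancies that were at risk of loss and then ended in induced abortion, which can bias the prevalence ratio when termination differs by vaccination

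*Protocol*

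**What the plan says.** Section 9.2.1 takes in pregnancies "ending in a live or still birth, a spontaneous abortion, an induced abortion, or an ectopic pregnancy". For fetal death (spontaneous abortion or stillbirth), Table 4 in section 9.7.2 narrows this to "A combined population of stillbirths, livebirths, and pregnancies ending in a spontaneous abortion", with exposure at any time during pregnancy. Elective termination and termination for fetal anomaly (TOPFA) are separate Table 4 outcomes analysed in all pregnancies, so the data are expected to contain them.

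Occurrence is a plain proportion: "Prevalence of each outcome will be computed as number of observations with a given outcome divided by the total number of study population members" (section 9.7.2). Section 9.1.1 adds "The measure of association will be prevalence ratio", and section 9.7.3 assigns "log-binomial regression for prevalences and risks and Cox proportional-hazards regression for incidence rate ratios". Exposure is set in section 9.3.1: "The exposure will be defined by a record of receipt of at least one dose of Spikevax during pregnancy". For stillbirth alone, section 9.7.1 says "For the outcomes of congenital malformations and stillbirth the number at risk will be the total number of live or stillborn children".

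No gestational time axis, censoring or competing-event handling is stated for fetal death. The limitations (section 9.9) mention undetected early losses and over-representation of short pregnancies, but not this restriction.

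**The concern.** Induced abortion prevents a later miscarriage or stillbirth, so it competes with fetal death. A pregnancy that miscarries in week 8 stays in the table as a case. One that survives week 8 and is terminated in week 10 was at risk in the same week without an event, yet it is removed. Fetal-death prevalence is then inflated, and more so in the group with more terminations.

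The exposure definition makes a difference between groups plausible: a pregnancy that ends early has less time in which a dose can be given, so terminations would tend to collect among the unexposed. The ratio would then lean below 1 and could hide a small harm in one of the primary outcomes. A larger sample does not remove such a shift.

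**Working it through.** **1. The plan's own precision figure.** Inputs from Table 3, largest database, spontaneous abortion: 16,667 exposed, 5 comparators per exposed, prevalence 0.2 in both groups, true ratio 1.

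SE(log PR) = √[((1−p)/p)(1/n₁ + 1/n₀)] = √[4 × (1/16,667 + 1/83,335)] = 0.0170

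Upper limit = exp[(1.96 + z) × 0.0170], which gives 1.049 with z = 0.842 (80%) and 1.057 with z = 1.282 (90%). Table 3 states 1.05 and 1.06. It reproduces, as do its other rows.

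**2. Two-stage model with no vaccine effect.** Loss risk is p = 0.20 (Table 3). The other inputs are assumptions, because the protocol gives neither: a share f of losses comes before the time of termination, and a share t of pregnancies still ongoing is then terminated, independently of later loss.

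- Losses = pf + p(1−f)(1−t)
- Births = (1−p)(1−t)
- Table 4 proportion = losses / (losses + births)
- All-pregnancies proportion = losses

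With f = 0.5, exposed t = 0.05 and unexposed t = 0.15:

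- Exposed: losses 0.10 + 0.10 × 0.95 = 0.195, births 0.80 × 0.95 = 0.760, proportion 0.195/0.955 = 0.2042
- Unexposed: losses 0.10 + 0.10 × 0.85 = 0.185, births 0.80 × 0.85 = 0.680, proportion 0.185/0.865 = 0.2139
- Table 4 ratio = 0.2042/0.2139 = 0.955
- All-pregnancies ratio = 0.195/0.185 = 1.054

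| Share of losses before termination (f) | Table 4 ratio | All-pregnancies ratio |
|---|---|---|
| 0 | 1.000 | 1.118 |
| 0.25 | 0.976 | 1.085 |
| 0.5 | 0.955 | 1.054 |
| 0.75 | 0.935 | 1.026 |
| 1 | 0.917 | 1.000 |

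Other assumed rates (exposed vs unexposed), over f from 0 to 1:

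- 2% vs 5%: Table 4 ratio 1.000 to 0.976
- 15% vs 5%: 1.000 to 1.091, so the direction reverses
- Equal rates: 1.000 throughout

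**3. Weekly model, varying which losses are recorded.** Assumptions: miscarriage hazard falling over weeks 5–20 (by 15% a week, by 25% a week, or linearly), scaled to a total risk of 10%, 15% or 20% and equal in both groups. Termination occurs in weeks 7–11 with weekly probability 1 − (1−t)^(1/5), at 5% exposed vs 15% unexposed.

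| Losses recorded from | Table 4 ratio (truth 1) |
|---|---|
| week 5 | 0.93–0.95 |
| week 8 | 0.96–0.97 |
| week 10 | 0.98–0.99 |
| week 12 | 1.00 |

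If the hazard does not fall at all, the first row becomes 0.97. With full recording, the all-pregnancies ratio is 1.02–1.05 for the falling hazards.

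**4. Against the stated precision.** At 20% risk with full recording, a ratio of 0.93–0.95 is ln(0.93)/0.0170 = −4.3 to ln(0.95)/0.0170 = −3.0 standard errors. That is as large as the 5–6% excess that Table 3 says can be ruled out. Recording only from week 10 leaves about one standard error or less. At 10% prevalence the SE is √[9 × (1/16,667 + 1/83,335)] = 0.025, so the same shift weighs less.

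**The case against.** The strongest counter-argument is early capture. Section 9.9 says early losses without a health-care record cannot be detected, and Table 5 describes the Norwegian birth registry as covering pregnancies of at least 12 weeks. Losses before the terminations drive the bias, and they are the ones least likely to be recorded. This stands, and it is why the size runs from about 7% down to nothing.

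A reader might infer that the ratio is biased whenever termination rates differ. It is not: with f = 0 it is exactly 1. A reader might also infer that the vaccine will look protective. The protocol gives no termination rates by vaccination, and the direction reverses if the exposed terminate more often.

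Ectopic pregnancies do not strengthen the point. They are not at risk of intrauterine loss or stillbirth in the same sense, so leaving them out is defensible.

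Nor is Cox regression already planned for this outcome. Section 9.7.3 reserves it for rate ratios, while fetal death belongs to the prevalence design. A Cox model by gestational age that kept the ever-exposed definition would count time before the dose as exposed and remain badly biased.

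Finally, section 9.3.2.1 leaves outcome-specific considerations to the SAP, and termination is itself reported by exposure. The SAP may add an analysis and a difference in termination would be visible, but Table 4 already fixes this population and nothing in the protocol corrects the ratio.

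**Conclusion.** The concern holds in conditional form. Table 4 selects pregnancies for the fetal-death denominator by how they ended, and the planned ratio has no time axis to repair that. Bias needs two things: termination that differs by vaccination, and recorded losses that precede terminations. Under an assumed 5% vs 15% and no true effect, the shift is about 5–7% with full recording from week 5, 1–2% with recording from week 10, and zero when terminations come before all recorded losses. At 2% vs 5% it is at most 2.4% in the two-stage model. A shift below 1 is the more plausible direction given the exposure definition, but the protocol does not establish it. Table 3 is arithmetically correct; it describes random error only, for crude single-database comparisons.

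**What to change.** In Table 4 and section 9.7.3, add for fetal death an analysis on the gestational-age scale:

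- Pregnancies ending in induced abortion, including TOPFA, contribute time until they end.
- Entry is when the pregnancy becomes identifiable, where that is known.
- Exposure varies with time and starts at the dose date, as section 9.1.2 already does for pregnancy-related death.
- Report the cause-specific hazard ratio, with Aalen-Johansen cumulative incidence for absolute risk and termination as a competing event.
- Show the current restricted prevalence ratio beside it.

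Ectopic pregnancies may stay excluded. Changing to an all-pregnancies denominator alone is not a remedy, because step 2 shows it errs in the opposite direction.

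The cost is modest programming and a hazard ratio as well as a prevalence ratio to explain. Reading that hazard ratio as the risk had no termination occurred needs an untestable independence assumption. No new data are needed: pregnancy start and end dates are already required (sections 9.1.1 and 9.2.2). Terminations are incompletely captured in some databases (only those with a hospital encounter in Denmark and Norway, section 9.2.1), and this should be stated as a limitation.
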